measurements collected in HD-YAS 2.0. Unless otherwise noted, outcomes are continuous or pseudo-continuous measures. By default, we will use general least-square linear models to evaluate possible overall group differences and age interactions between the young adult premanifest HD gene carriers and controls. Within these same models, we will control and test possible CAG-length-driven differences within premanifest HD gene carriers. Covariates will include age, gender, site and age interactions with gender. The main hypothesis of group differences will be evaluated by least-square means.

The primary cross-sectional analyses model will have a nearly identical generic form to that used in the original baseline analysis:

$$y = b_0 + I_{pHD} * (b_1 + b_2 * CAG + b_3 * age + b_4 * CAG * age) + b_5 * age + b_6 * sex + b_7 * age * sex + b_8 * NART + b_9 * EducLevel + r_{subject} + e$$

where y is an outcome variable, $I_{pHD} = 1$ if a participant is from the premanifest HD gene carrier group and 0 otherwise, the b 's are linear regression coefficients, $r_{subject}$ is a subject-specific random effect applicable to participants who have had two measurements, and e is the residual random error term. Both $r_{subject}$ and e are assumed to be independently, identically normally distributed among the participants with 0 mean. (See above for contingencies when these distributional assumptions prove empirically untenable.) Note that NART score (a proxy for estimated baseline IQ) and education level will only be used for cognitive outcomes.

Hypothesis 2: There is evidence of disease-related *longitudinal* change ~20 years from expected symptom onset in: a) brain imaging; b) cognition; c) neuropsychiatric function; and d) biofluid measures.

The longitudinal analyses will build on the above model by adding these further regression terms:

$$a_0 * follow-up + I_{pHD} * follow-up * (a_1 + a_2 * CAG + a_3 * age + a_4 * CAG * age) + follow-up * (a_5 * age + a_6 * sex + a_7 * age * sex + a_8 * IQ,)$$

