where the regression coefficients a. estimate the longitudinal influence of follow-up time with the covariates listed in the original cross-sectional model. One other difference between the cross-sectional and longitudinal analyses is that the cross-sectional analysis will use age at each visit as a covariate, whereas the longitudinal analysis will use age at baseline. This is because changes of age with follow-up and length of follow-up are redundant measures. A readily interpreted assessment of observed longitudinal change with follow-up requires that the age term in the model remains constant.

Boundary Shift Intervals (BSI) measures of MRI volumetric change will require a modification to the above longitudinal model, since these are a direct estimate of change between two MRI scans. Boundary shift volumes will be divided by time between the MRI scans, and the resultant statistic will be used as a volume change rate. This volume change rate will be the outcome variable, y, subjected to analysis.

$$y = b_0 + I_{pHD} * (b_1 + b_2 * CAG + b_3 * age + b_4 * CAG * age) + b_5 * age + b_6 * sex + b_7 * age * sex + b_8 * IQ + e$$

The age term in this BMI model again represents baseline age for the participants, to avoid confounding of changing age and follow-up time in the study. Since there will at most a single BMI measure per participant, the model will contain only a simple residual error term. No subject-specific random effects are estimable.

Hypothesis 3: Early pathological events lead to impairment in isolated functional domains such as cognitive flexibility.

Statistical analyses will only examine potential associations between early pathological events and functional impairment. Issues of causality will remain the subject of logical scientific conjecture. Analyses will be limited to combinations of pathological measures and functional measures that demonstrate differences between the HD gene carriers and controls, per the mixed model analyses described above to address Hypotheses 1 and 2.

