For the functional measures used, we will assess both cross-sectional and lagged associations with pathological measures using the combined data from HD-YAS 1.0 and HD-YAS 2.0. To test cross-sectional associations, we will add the contemporary pathological measures as additional potential predictors in the cross-sectional models of the form defined above for hypothesis 1. These analyses will be limited to only the HD gene carriers and will therefore not include terms for HD-carrier versus control status or interactions of that genetic status.

We will further test for a potential lag between pathological events and measurable impairment using only the cross-sectional data impairment data from HD-YAS 2.0. Analyses will be limited to those from the HD-YAS 1.0 who also participated in HD-YAS 2.0. With single HD-YAS 2.0 functional observations per participant, we will estimate ordinary least squares regression models using both the baseline and follow-up (HD-YAS 2.0) pathology measures. (Subject to potential adjustments for violation of mathematical modeling assumptions as discussed in the General Methods section above). We will test for an association between HD-YAS 1.0 pathology measures and HD-YAS 2.0 functional measures. We will further estimate the joint associations of the HD-YAS 1.0 and HD-YAS 2.0 pathology measures by including both as joint predictors of the functional outcome. We will also refit the models by re-parameterizing the 1.0 and 2.0 values as the 1.0 value and the change in the pathology measure between 1.0 and 2.0. Other covariates in these models will be the same as described for the previous analyses (age, sex, CAG length, CAG by age interaction, and in the case of cognitive functional measures, baseline NART and Education level scores).

Within the premanifest HD gene carrier group, we will determine how well the clinical and neuroimaging variables are predicted by CSF levels of mHTT and by CSF and plasma levels of NfL. Analyses will be performed one biomarker one at a time and have the general form:

$$y = b_0 + b_1 * \text{biomarker} + b_2 * \text{age} + b_3 * \text{gender} \\ + b_4 * \text{age} * \text{gender} + b_5 * \text{IQ} + r_{\text{subject}} + e$$

Additionally, we will assess evidence of longitudinal prediction of change in HD measures by adding the additional terms to the above model.

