$$\begin{aligned} & \text{follow-up} * (a_1 + a_2 * \text{CAG} + a_3 * \text{age} + a_4 * \text{CAG} * \text{age}) + \\ & \text{follow-up} * (a_5 * \text{baseline biomarker}) + a_6 * \text{biomarker change from baseline}, \end{aligned}$$

Hypothesis 4: Individuals with higher levels of somatic CAG-repeat expansion are more vulnerable to early striatal atrophy, breakdown of corticostriatal connections and cortical pathology.

We will analyse potential relationships between somatic expansion and other HD measures using the same models described immediately above for hypothesis 3.

Hypothesis 5: Measures identified as showing disease sensitivity in hypotheses 1 and 2 have utility for future trials of disease-modifying therapy in premanifest HD gene carriers.

We will calculate nominal sample size estimates for longitudinal measures showing relationship to HD gene expansion vs. controls or longitudinal relationships to the severity of combined age and CAG genetic risk. We will perform such calculations for measures with longitudinal change below the 15% estimated false discovery rate. We note however, that this screening for evidence of disease sensitivity will tend to optimistically bias such estimates towards smaller sample sizes. The resultant sample sizes will therefore represent an estimated lower bound.

We will consider the following 5 biomarkers as primary outcomes for these analyses, as previous data, including baseline data from YAS 1 have suggested cross-sectional relationships between these measures and early HD disease pathology:

1. Putamen volume change
2. Caudate volume BSI
3. CSF NfL levels
4. Plasma NfL levels

5. CSF mHTT levels

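### In the Hypothesis 3 and 4 longitudinal biomarker model, as most naturally read, the coefficient labelled biomarker change (a6) is not the change association, which is b1 + a6; the SAP should label the visit for b1 or name the tested contrast.

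*SAP*

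**What the plan says.** The biomarker models are in the SAP under Hypothesis Testing, Hypothesis 3, and are limited to gene carriers. They take CSF mHTT and CSF and plasma NfL one at a time. The base model is y = b0 + b1 × biomarker, plus age, gender, age by gender and IQ terms, a subject random effect and a residual. The SAP defines that random effect under Hypothesis 1: it "is a subject-specific random effect applicable to participants who have had two measurements". The model therefore has one row per visit.

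For the longitudinal version, "we will assess evidence of longitudinal prediction of change in HD measures by adding the additional terms to the above model". The added terms are follow-up by CAG and age terms (a1 to a4), follow-up × a5 × baseline biomarker, and a6 × "biomarker change from baseline". The a6 term is not multiplied by follow-up. Nothing is removed from the base model and b1 × biomarker is not redefined.

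One covariate is explicitly moved to its baseline value for longitudinal work, under Hypothesis 2: "the cross-sectional analysis will use age at each visit as a covariate, whereas the longitudinal analysis will use age at baseline". No such move is stated for the biomarker.

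Hypothesis 4 adds no model of its own: "We will analyse potential relationships between somatic expansion and other HD measures using the same models described immediately above for hypothesis 3". No coefficient or contrast is named as the test of biomarker change under either hypothesis.

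**The concern.** The added terms name the baseline biomarker separately from the biomarker in the b1 term. The natural reading is that b1 multiplies the value at each visit. The model then holds the current biomarker and its change from baseline side by side, and the current value already contains the change. The change effect is split between b1 and a6.

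An analyst working from the printed equation would be inclined to look at a6, the only term labelled as change, to judge whether biomarker change tracks outcome change. Read that way, a6 can be near zero when a real change association exists. It can also be clearly non-zero with the opposite sign when only a cross-sectional association exists. The questions affected are whether changes in mHTT, NfL and somatic expansion go along with changes in imaging and clinical measures. Section 8 of the Protocol promises that all analyses will be prespecified in the SAP, so the intended estimand should be stated there.

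**Working it through.** The documents give no power, error rate or effect size for this model, so there is no figure to reproduce. The main result is algebra.

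**Algebra.** Let B0 be the baseline biomarker, D its change, and t the follow-up time. The current value is B0 at baseline and B0 + D at follow-up.

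- Baseline row: b1·B0 + other terms.
- Follow-up row: b1·(B0 + D) + a6·D + a5·t·B0 + other terms = b1·B0 + (b1 + a6)·D + a5·t·B0 + other terms.
- Difference: E[y1 − y0] = (b1 + a6)·D + a5·t·B0 + follow-up by CAG and age terms.

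The within-person slope is b1 + a6. The between-person slope is b1. Hence a6 = within-person slope − between-person slope. It equals the within-person slope only if b1 = 0, yet the base model exists to estimate b1.

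**With the baseline biomarker in the b1 term.** The follow-up row is b1·B0 + a6·D + a5·t·B0, so a6 is itself the within-person slope. This is the same fitted model with its coefficients relabelled.

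**Simulation 1.** Inputs from the SAP (overview, The Cohort): 57 returning carriers, 64 − 57 = 7 who did not return, 9 new carriers, follow-up of about 4.5 years. That gives 57 two-visit and 7 + 9 = 16 one-visit carriers. Assumed, not in the documents: baseline biomarker SD 1, change mean 0.5 and SD 0.6, random-intercept SD 0.8, residual SD 0.4. A random-intercept model was fitted by REML to 60 data sets per row, with significance at |z| > 1.96.

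| Between slope | Within slope | Mean a6 as printed (significant) | Mean b1 + a6 (significant) |
|---|---|---|---|
| −0.4 | −0.4 | −0.01 (3%) | −0.39 (87%) |
| −0.4 | −0.2 | +0.20 (22%, all positive) | −0.19 (27%) |
| −0.4 | 0 | +0.38 (63%, all positive) | −0.01 (8%) |
| −0.2 | −0.4 | −0.21 (30%) | −0.42 (87%) |
| −0.4 | −0.6 | −0.18 (18%) | −0.61 (100%) |
| 0 | −0.4 | −0.40 (67%) | −0.39 (88%) |

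The printed model is estimable (rank 12 of 12 columns). In every data set, b1 + a6 from the printed form matched a6 from the baseline form to within 3e-15, and a5 was the same in both. With 60 runs the Monte Carlo error is up to about 6 percentage points (√(0.5 × 0.5 / 60) = 0.065).

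**Simulation 2.** This used 49 carriers with paired CSF (0.86 × 57 = 49), 4.5 years, a correlation of 0.7 between outcome visits, SD of change 0.6 baseline SDs, and 1,000 replicates. The 49 and the effect sizes are assumptions.

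- Between = within = 0.4: a6 as printed averages 0.01 and rejects in 5%; with baseline in the b1 term, 0.40 and 60%.
- Between 0.4, within 0: a6 as printed averages −0.41 and rejects in 42%; with baseline in the b1 term, −0.01 and 6%.

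**The case against.** The strongest reply is that the SAP does not commit to the faulty test. It speaks of adding terms in the plural and names no coefficient. A reader might infer that the plan will report a null or false change association; the documents do not support that, because nothing says a6 will be tested alone. This stands, and it makes the consequence conditional.

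Second, the visit for b1 is not labelled, and the equation is given only as a general form. It is visibly shorthand: follow-up by CAG is added although the base model has no CAG main effect. If b1 was meant to carry the baseline value, the printed model is already right. This also stands as a possibility, but the separate naming of the baseline biomarker, and the switch to baseline stated for age alone, point the other way. It might be said that the a5 interaction needs a baseline main effect and so b1 must be baseline. That does not settle it, since the current value and the change together already span the baseline value.

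Third, a reader might infer that the model is biased or that Hypotheses 3 and 4 cannot be answered. Neither follows. Both forms give the same fit, b1 + a6 can be recovered from it, and a5 is untouched. Whether the baseline biomarker predicts later rate of change is arguably the most literal sense of longitudinal prediction.

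Fourth, the stakes are bounded. The SAP limits Hypothesis 3 to associations. The Hypothesis 1 and 2 group comparisons do not use this model, and the Hypothesis 5 sample sizes come from models with follow-up as the only fixed effect. The Hypothesis 3 lag analysis is already refitted with the 1.0 value and the change, though it is a different model, on 2.0 functional outcomes only.

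Last, the 86% behind the 49 paired carriers describes CSF collection in the whole follow-up cohort. It is neither carrier-specific nor a paired-sample rate, and it does not apply to plasma NfL or blood DNA.

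**Conclusion.** The point holds as a specification gap that should be fixed before analysis. On the most natural reading, the change association is b1 + a6, and a6 alone is the within-person minus the between-person association. That follows from the algebra and rests on no assumed number. It does rest on reading b1 as multiplying the value at each visit, which the SAP does not say outright.

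How much a6 alone would mislead depends on effect sizes, SDs and the number of paired samples, none of which the documents give. Across the two simulations, equal effects gave 3–5% rejection for a6 against 60–87% for the change association. A between-person effect only gave 42–63% false rejection against 6–8%. When the between-person slope is zero, a6 is right on average.

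**What to change.** In the longitudinal version of the Hypothesis 3 biomarker model, replace b1 × biomarker with b1 × baseline biomarker and keep a5 and a6. Then b1 is the between-person level association, a5 is baseline biomarker predicting rate of change, and a6 is biomarker change tracking outcome change. Alternatively, keep the printed model, state that b1 uses the value at each visit, and prespecify b1 + a6 as the test of biomarker change. State that the same form applies to somatic expansion under Hypothesis 4.

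This is a one-term edit or one added sentence. It needs no new data, visits or assays, and it leaves the fit and a5 unchanged.

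### Hypothesis 4 has no written model, and the form directly above it omits CAG main effects, so somatic expansion may not be separable from inherited CAG length

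*SAP*

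**What the plan says.** In the SAP, Hypothesis Testing, Hypothesis 4 states that "Individuals with higher levels of somatic CAG-repeat expansion are more vulnerable to early striatal atrophy, breakdown of corticostriatal connections and cortical pathology". Its analysis text is one sentence: "We will analyse potential relationships between somatic expansion and other HD measures using the same models described immediately above for hypothesis 3".

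Hypothesis 3 contains three families of models.

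- **Contemporary pathology models.** Here "we will add the contemporary pathological measures as additional potential predictors in the cross-sectional models of the form defined above for hypothesis 1". The Hypothesis 1 form nests CAG and CAG × age within the carrier group, so both remain when the analysis is restricted to carriers.
- **Lagged models.** The text reads "Other covariates in these models will be the same as described for the previous analyses (age, sex, CAG length, CAG by age interaction", and continues with further covariates for cognitive outcomes.
- **One-biomarker models**, the last before Hypothesis 4. They ask "how well the clinical and neuroimaging variables are predicted by CSF levels of mHTT and by CSF and plasma levels of NfL". The SAP adds: "Analyses will be performed one biomarker one at a time and have the general form". The form contains the biomarker, age, gender, age × gender, IQ and a random subject effect. Its longitudinal extension adds follow-up multiplied by CAG, age and CAG × age, then follow-up × baseline biomarker (coefficient a5) and biomarker change (a6). CAG enters only through products with follow-up.

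The BSI model under Hypothesis 2 has CAG and CAG × age as main effects.

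**The concern.** Somatic expansion is growth of the same repeat whose inherited length the SAP treats elsewhere as a possible cause of differences among carriers. If expansion correlates with inherited length given age, sex and IQ, a model without CAG gives expansion the credit for whatever CAG does to the outcome. The expansion ratio is expressed relative to baseline repeat length, but that is not regression adjustment and need not remove the correlation.

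Hypothesis 4 is worded in terms of vulnerability. A positive level result would easily be read as showing that expansion adds something beyond the inherited repeat. The one-biomarker form cannot show that.

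Section 8 of the protocol promises that all analyses will be prespecified in the SAP. As the text stands, two analysts could follow it and fit different Hypothesis 4 models.

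**Working it through.** **1. Where CAG appears**

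| Model | CAG main effect | CAG × age main effect | CAG × follow-up |
|---|---|---|---|
| Hypothesis 1, cross-sectional | yes | yes | not applicable |
| Hypothesis 2, longitudinal | yes | yes | yes |
| Hypothesis 2, BSI | yes | yes | not applicable |
| Hypothesis 3, contemporary | yes | yes | not applicable |
| Hypothesis 3, lagged | yes | yes | not applicable |
| Hypothesis 3, one biomarker | **no** | **no** | only in the extension |
| Hypothesis 4 | not written | not written | not written |

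**2. Which family Hypothesis 4 means.** The cross-reference is plural, so the first two Hypothesis 3 families are possible. They are written for functional outcomes, whereas Hypothesis 4 concerns striatal, connectivity and cortical outcomes. They also carry a restriction: "Analyses will be limited to combinations of pathological measures and functional measures that demonstrate differences between the HD gene carriers and controls". Expansion cannot meet it, because controls give no DNA sample (protocol section 12, DNA for Research Genotyping). This favours the one-biomarker form without settling the matter.

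**3. Inputs for the illustration**

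- Carriers: 66, of whom 57 returned and 9 are new (SAP, The Cohort). With MRI: 66 × 0.91 ≈ 60, assuming the 91% applies equally to both groups.
- Test level 5% (protocol section 8); two-sided is assumed.
- CAG–outcome correlation r: 0.36 or 0.2, both assumed. The value 0.36 is the protocol's detectable partial correlation for 60 carriers with 5 covariates, used only as a scale. It is reproducible: f² = 0.1296/0.8704 = 0.149, 53 error degrees of freedom, noncentrality 55 × 0.149 = 8.19, power 80.2%. Other standard variants give about 78 to 84%.
- Expansion–CAG correlation ρ: not in the documents; 0, 0.3, 0.5 and 0.7 assumed.

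The SAP gives no figure for Hypothesis 4 to reproduce.

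**4. Expected bias.** If expansion has no effect given CAG, the unadjusted standardised coefficient is about r × ρ. For r = 0.36 and ρ = 0.5 this is 0.18 (simulated: 0.183). By the Fisher z approximation with 66 carriers and 4 covariates, the rejection rate is Φ(atanh(0.18) × √59 − 1.96) = Φ(1.398 − 1.96) = Φ(−0.56) ≈ 0.29.

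**5. Simulation.** Least squares, one observation per carrier, outcome = r × CAG + noise, 20,000 replicates per cell (Monte Carlo standard error at most 0.35 points). Rejection rates for the expansion coefficient in the one-biomarker form, in per cent:

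| n | r | ρ = 0 | 0.3 | 0.5 | 0.7 |
|---|---|---|---|---|---|
| 66 | 0.36 | 5.0 | 13.5 | 28.9 | 50.6 |
| 66 | 0.2 | 4.9 | 7.6 | 12.2 | 19.0 |
| 60 | 0.36 | 5.1 | 12.0 | 27.7 | 47.1 |
| 60 | 0.2 | 5.0 | 7.1 | 11.2 | 18.0 |

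With CAG and CAG × age added, every cell lies between 4.8 and 5.2. If CAG and age correlate at −0.5 and the other correlations are taken given age, the figures for n = 60, r = 0.36 are 12.0, 26.7 and 47.5 at ρ = 0.3, 0.5 and 0.7.

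**6. Do the follow-up terms repair this?** For the level coefficient, no. With 57 carriers seen twice and 9 once, r = 0.36, an assumed intraclass correlation of 0.8 and the written follow-up terms included, its rejection rates are 6.4, 15.2, 32.6 and 54.0% (3,000 runs). With the CAG main effects they are 4.7 to 5.7%. The slope coefficient a5, which sits beside follow-up × CAG, is largely clean for reliable outcomes: about 5 to 7% at intraclass correlations of 0.8 to 0.9. At 0.4 it rose to about 6 to 13% across two checks.

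**7. Price of adjustment.** The standard error grows by 1/√(1 − ρ²): 1.05, 1.15 and 1.40 at ρ = 0.3, 0.5 and 0.7. For a true standardised expansion effect of 0.36 and no direct CAG effect, power falls from about 83% to 79, 70 and 54% at n = 66, and from about 79% to 73, 66 and 50% at n = 60.

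**The case against.** The strongest reply is that Hypothesis 4 promises only an analysis of potential relationships, and under Hypothesis 3 the SAP says that "Issues of causality will remain the subject of logical scientific conjecture". If the target is a plain age-adjusted association, an association carried by CAG is real and not a false positive. That is right. The rates above apply only to the question of whether expansion adds anything beyond inherited CAG. But the hypothesis wording invites that reading, so the result must at least be labelled.

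Second, two of the three Hypothesis 3 families adjust for CAG, and protocol section 8 lists CAG and its interaction with age as carrier covariates for the group comparisons. This shows the study's convention, and the authors may have intended it here. It does not tell the analyst which family to use.

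Third, both correlations are assumed, and at ρ = 0 there is no inflation. This stands: the figures are a range, not a prediction.

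Fourth, adjustment costs power, and if expansion carries much of CAG's effect it mainly loses precision. This also stands, and is a reason to report both coefficients. It is not a reason to leave the model unwritten.

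**Conclusion.** The concern holds. Hypothesis 4 leaves its model to a cross-reference, and the nearest form is the only one in the Hypothesis Testing section without CAG main effects. If that form is used, the level coefficient of expansion is confounded by inherited CAG to the extent that the two correlate given the other covariates. Under the assumed correlations of 0.3 to 0.7, the rejection rate with no effect beyond CAG is about 14 to 51% (r = 0.36) or 8 to 19% (r = 0.2) with 66 carriers, and about 12 to 47% or 7 to 18% with 60.

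The defect is limited to that reading and mainly to level outcomes. The slope coefficient is little affected for reliable measures, and BSI outcomes already have a model with CAG, which needs only to be confirmed as the one used. For NfL and mHTT the stated question is prediction, so a result without CAG is acceptable there if labelled. This should be corrected before the Hypothesis 4 analysis is run.

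**What to change.** - Write out the Hypothesis 4 model. Include CAG and CAG × age as main effects in both the cross-sectional form and the longitudinal extension, and name the CAG-adjusted expansion coefficient as the level test. The same terms also protect the slope coefficient for less reliable outcomes.
- For BSI outcomes, confirm that the Hypothesis 2 BSI model is used, restricted to carriers and with the expansion term added.
- Report the coefficient without CAG beside it, labelled as descriptive.
- State whether the biomarker term in the extension is the baseline or the visit value.
- If the other Hypothesis 3 families were intended, say so and list the outcomes.

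This is a change of SAP wording. CAG length is already measured in carriers and used in the other models. The statistical cost is two degrees of freedom and the loss of precision shown in step 7 of the working.

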Estimates of sample size requirements will be based upon the estimated longitudinal effect sizes (mean slope divided by between-subject slope standard deviation) calculated from mixed effect longitudinal. The models will be limited to HD gene-expanded participants and follow-up time will be the sole fixed effect. (The resultant estimates of natural history change will thus represent the relevant average natural history progression among the entire group of CAG-expanded participants. Additional effects of potential stratification are discussed shortly below.) Initial calculations will assume 5- and 10-year trials with annual follow-up, 50 and 70% slowing due to treatment, no placebo effect, and use of slopes rather than net change of outcome from the beginning to end of the trials. We will assume no drop-out and that the within-subject outcome variance does not increase over time. These conditions will yield best-case estimates for idealized trials. For any measure, should the resultant sample sizes appear hypothetically feasible, we will perform follow-up calculations assuming 2-, 3-, and 4-year trials with similar and smaller treatment effect sizes.

Potential trial enrichment: For the potential trial outcomes used in the above analyses, we will further test whether the possible stratification criteria of HD-ISS stage of 1 or greater (versus 0) or CAP100 score of 100 or greater are significantly associated with different rates of natural history longitudinal change. We will repeat the sample size analyses described in the previous paragraph with the data limited to the subset of CAG-expanded participants meeting the stratification criterion in question.

Table 1: Outcome variables by modality

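### Hypothesis 5 applies treatment slowing to the carriers' total slope, so change shared with controls can count as treatable; its effect size cannot be computed for caudate BSI and, as written, ignores trial length

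*SAP*

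**What the plan says.** Hypothesis 5 of the SAP gives a method and no sample size.

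- **Data and model.** "The models will be limited to HD gene-expanded participants and follow-up time will be the sole fixed effect". The SAP describes the result as the average natural history of the whole carrier group.
- **Effect size.** It is the "mean slope divided by between-subject slope standard deviation", taken from a mixed longitudinal model.
- **Trial conditions.** "Initial calculations will assume 5- and 10-year trials with annual follow-up, 50 and 70% slowing due to treatment". Slopes are to be used rather than net change, with no placebo effect. "We will assume no drop-out and that the within-subject outcome variance does not increase over time". Calculations for 2, 3 and 4 years follow if the first sizes look feasible.
- **Primary outcomes.** Putamen volume change, caudate BSI, CSF NfL, plasma NfL and CSF mHTT.
- **Role of controls.** They help to select measures, through an estimated false discovery rate below 15%. No control slope is subtracted from the slope that is sized.
- **Labels.** The sizes are called nominal. They are called a lower bound because of the screening, and best-case because of the idealised trial conditions.

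Two parts of Hypothesis 2 bear on this. For its longitudinal model, "The longitudinal analyses will build on the above model by adding these further regression terms"; those terms include a follow-up slope common to both groups and a separate carrier-specific slope. For the boundary shift integral, "Boundary shift volumes will be divided by time between the MRI scans, and the resultant statistic will be used as a volume change rate". The SAP then says: "Since there will at most a single BMI measure per participant, the model will contain only a simple residual error term" (BMI is evidently a slip for BSI). It adds: "No subject-specific random effects are estimable".

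**The concern.** The sizes serve the secondary objective in Protocol 3.2, which is to find the measures most useful for trials. Three features of the method affect that use.

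First, a treatment aimed at Huntington's disease can be expected to slow disease-related change, not the change that controls also show. If part of the carriers' slope is shared with controls, 50% slowing of the total slope asks more of the treatment than 50% slowing of the disease. The understatement of N can differ from one measure to another, so it can alter their ranking as well as their level.

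Second, the SAP requires for caudate BSI a quantity that its own BSI model says does not exist. Hypothesis 2 adapts its model for BSI; Hypothesis 5 has no matching adaptation.

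Third, the effect size has no place for trial length or visit schedule, although the SAP lists five trial lengths and annual visits. The mention of within-subject variance shows that a residual term is intended, but no formula combines it with the slope variance. The only random effect written in the Hypothesis 1 and 2 models is a single subject effect; no random slope is specified.

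**Working it through.** There is no Hypothesis 5 figure to reproduce. No slope, SD, alpha, power or allocation is given for it. The illustrations below assume two-sided 5%, 80% power and 1:1 allocation.

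**1. Shared change.** Let f be the fraction of the carrier slope also seen in controls. N varies as 1/(treatment difference)². If only the remainder is treatable and the SD is unchanged, needed N over planned N is 1/(1−f)².

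- f = 0.1: 1/0.9² = 1.23
- f = 0.3: 1/0.7² = 2.04
- f = 0.5: 1/0.5² = 4.0

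These values of f are assumptions. CSF mHTT is exempt, because the SAP's section on the mutant huntingtin assay takes it as 0 in controls by definition.

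**2. The effect size read literally.** With E = mean slope / slope SD and slowing p, n per arm = 2(1.960 + 0.842)²/(pE)². An assumed E = 1 gives 63 at 50% slowing and 33 at 70%, whatever the trial length.

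**3. With residual variance.** For annual visits over T years, Sxx = T(T+1)(T+2)/12, which is 2, 5, 10, 17.5 and 110 at 2, 3, 4, 5 and 10 years. The variance of an estimated slope is var_slope + var_e/Sxx, so n is multiplied by 1 + q/Sxx with q = var_e/var_slope. At E = 1 and 50% slowing, with q assumed:

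| Trial length | q = 1 | q = 10 | q = 50 |
|---|---|---|---|
| 2 years | 95 | 377 | 1633 |
| 5 years | 67 | 99 | 243 |
| 10 years | 64 | 69 | 92 |

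**4. Caudate BSI.** The SD of the annualised rate is available. Treat the rate as a two-scan difference over about 4.5 years with independent error per scan. Its variance is then var_slope + 2·var_e/4.5² = var_slope + var_e/10.125. If s is the share of that variance due to true slopes, the variance needed for a T-year trial is the observed one times s + (1−s)·10.125/Sxx. With s assumed at 25% and 75%:

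| Trial length | Multiplier (s = 25%, 75%) | N from unconverted SD over needed N |
|---|---|---|
| 2 years | 4.05, 2.02 | 0.25, 0.50 |
| 3 years | 1.77, 1.26 | 0.57, 0.80 |
| 4 years | about 1.0 | about 1.0 |
| 5 years | 0.68, 0.89 | 1.46, 1.12 |
| 10 years | 0.32, 0.77 | 3.13, 1.29 |

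**5. Can two visits supply the split?** Two visits at a common interval give three moments (two variances and a covariance). A random intercept and slope model with residual error has four parameters (intercept variance, slope variance, their covariance, residual variance). For example, variances of 10 and 10.5 with covariance 8, at 4.5 years, fit residual variances of 0.5, 1 and 2 equally well, with slope variances of 0.173, 0.123 and 0.025. Varying intervals help little. In simulations with 49 or 52 carrier pairs, 20 single values and an interval SD of 0.3 or 0.6 years, under assumed variances, the slope SD was estimated below a quarter of its true value in 16–30% of datasets.

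**6. Precision of a control-adjusted slope.** The SAP's cohort section gives 57 carriers and 45 controls with two visits. With equal SDs, the standard error of the slope difference is sqrt(1 + 57/45) = 1.51 times that of the carrier slope. If the 91% with MRI applies evenly and baseline scans exist, there are about 52 and 41 pairs. The standard error is then sqrt(1/52 + 1/41) = 0.209 rate SDs, against sqrt(1/52) = 0.139 for carriers alone. At an assumed slope of 0.8 rate SDs, the 95% limits on N, (0.8/(0.8 ± 1.96·SE))², are ×0.44 to ×4.19 for the difference and ×0.56 to ×2.29 for carriers alone.

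**The case against.** The strongest defence is that this is a declared choice. The SAP says that the slope is natural history in all carriers, treats the slowing as a scenario, and labels the results nominal, best-case and a lower bound. Where controls change in the same direction, the error runs the way those labels warn. Measures must also pass a screen for a relation to gene expansion or to age and CAG risk, which favours disease-related change. The control-adjusted N is less precise, and its interval is wider than most of the correction that it offers. Much of this stands: a carriers-only figure is defensible as one of two. But neither label is tied to shared change, the screen does not remove it, and a general caveat cannot correct a factor that may differ by measure.

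On caudate BSI, the natural reading is to use the mean and SD of the annualised rate. That is right, but Hypothesis 5 does not say so, and that SD carries error at one interval only. The conversion in step 4 assumes independent error per scan, which the documents do not establish.

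The weak separation of the variances is largely a limit of two visits, which no wording can cure. The formula and a sensitivity range can still be stated.

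Two stronger readings are tempting. One is that normal ageing certainly makes every N too small. The documents give no control slope, so this cannot be said; if controls moved the other way, f would be negative and N too large. The other is that putamen and caudate would be sized from different kinds of SD, because Table 1 lists no change measure for putamen. But Hypothesis 5 names putamen volume change, and the imaging section of the Protocol plans putamen change over time. How that change is derived is unclear, so the inference is not supported.

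**Conclusion.** The point holds in three parts.

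- **Shared change.** The method counts it as treatable wherever controls change in the same direction. The factor is 1/(1−f)². The values 1.23 to 4.0 rest wholly on assumed f, on a treatment that acts only on the excess, and on an unchanged SD.
- **Caudate BSI.** The contradiction within the SAP is certain and needs no assumption. The direction of the error from an unconverted SD (N too large at 5 and 10 years, too small at 2 and 3) follows if error is independent per scan. Its size depends on the assumed s.
- **Unwritten formula.** That the literal ratio does not depend on trial length is certain. How much this matters depends on the ratio of residual to slope variance, which the documents do not give and two visits hardly identify.

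Confidence is high on the textual gaps and low on the magnitudes. Because the variance error can run either way, the lower-bound label is not assured on that account. The consequence is confined to what Hypothesis 5 can conclude about trial utility. Hypotheses 1 to 4 are not affected. The point should be fixed before the sizes are reported.

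**What to change.** (a) For putamen, caudate BSI, CSF NfL and plasma NfL, report N with slowing applied to the carrier-minus-control slope, with its confidence interval, beside the planned total-slope N. Leave CSF mHTT as it is.

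(b) For caudate BSI, size from the mean and SD of the annualised rate. State that this SD includes measurement error at about 4.5 years, and in which direction it tends to bias N at each trial length if left unconverted.

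(c) State the random-effects structure. Use slope variance plus residual variance divided by Sxx for each trial length. Show a sensitivity range for the split between the two variances; the range is the statistician's choice. The third timepoint foreseen in Protocol Section 3 would allow an update.

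(d) Beside the lower-bound sentence, name change shared with controls and the weakly identified slope SD.

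The cost is a few sentences, one extra column and a small sensitivity table, with no new data. The price of (a) is a less precise figure, with a standard error about 1.5 times that of the carrier slope, which is why it should stand beside the planned N and not replace it.
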